6. STUDY PROCEDURES

Study Outline

Pre-screening Procedures:

During the pre-screening process, the subject can contact a co-investigator, usually via encrypted Zoom Enterprise call, and REDCap form. During the pre-screening process, the co-investigator will discuss the details of the study, explain the study procedures, and encourage the subject to ask questions. In the privacy of the encrypted Zoom Enterprise call for healthcare, the co-investigator will ask the subject questions from the following:

- 1) Online Screening questionnaire
- 2) Phone Pre-screening questionnaire

Once this information is collected, the co-investigator will consult with the PI regarding the eligibility of the subject, who will then give the approval for the subject to come to our laboratory for the screening procedure.

Visit 1

Online or in-person Screening and Consent Visit – (Approximate Time: 1 hour)

If in-person, the visit 1 can be performed together with the visit 2 - (Approximate Time: 3 hours and 30 min).

If done remotely; the documentation would be signed electronically, and the visit would be done by telephone or using Zoom Healthcare)

During the Screening, the PI and/or a co-investigator will conduct once more a review of inclusion/exclusion criteria to determine the subject's eligibility for enrollment. If the consent is conducted by the co-investigator, the PI will review and sign off. Study procedures will be reviewed with the subject, and documentation of informed consent will be obtained. We will use an encrypted web-based platform (REDCap e-consent module) via Zoom call (Enterprise plan). Both services are already validated and in use by the MGB network.

- Discuss study-specific procedures with the subject.
- Review inclusion and exclusion criteria.
- Obtain a signed and dated consent form.
- Conduct a Demographics Survey, Brief Medical History, Beck depression inventory (BDI), and the Edinburg Handness Inventory Short form (EHI/SF).

Visit 2

Baseline Visit and First taVNS session – (Approximate Time: 2 hours and 30 min).

Urine pregnancy exam (if applicable).

Baseline assessments:

- EEG
- HRV
- QST
- The Brief Mood Introspection Scale (BMIS)
- Visual Analogue Scale to Evaluate Fatigue Severity (VAS-F) adaptation using tiredness item.

After the Baseline assessments:

Subjects will receive one session of either active taVNS or sham taVNS for 60 min. During the stimulation both groups will also be assessed with EEG, HRV, and VAS-F.

After the session, subjects will complete the following assessments:

- Side Effects Questionnaire for taVNS.
- Questionnaire to assess the success of blinding in clinical trials.
- EEG
- HRV
- QST
- BMIS
- VAS-F

Upon arrival and prior to the application, taVNS intensity will be measured for each participant separately, as above the detection threshold and below the pain threshold. The stimulation electrodes will be applied bilaterally to the ears, and in order to individually adjust the stimulation intensity, participants will receive increasing and decreasing series of 10-s stimulation trials and will rate the subjective sensation of the stimulation in a 10-point scale, ranging from nothing (0), light tingling (3), strong tingling (6), to painful (10). The increasing series of trials will start from an intensity of 0 mA and increase by 0.3 mA on a trial-by-trial basis until participants report it is uncomfortable to continue. This procedure will be repeated a second time. The final stimulation intensity for the experimental procedure will be calculated based on the average of the two intensities just below pain threshold.

We will use a Healaon Transcutaneous Auricular Vagus Nerve Stimulation (taVNS) device (Neurive Inc., Gimhae, South Korea), which consists of an earset, with conductive eartips placed on the auricular concha of the ears. Electrodes are connected to a stimulator, and during active stimulation, both the cyma conchae of the auricular are stimulated at 30Hz, 200-250 us, with adjustable intensity for 60 min. The sham intervention will be done at the same location bilaterally to the cyma conchae of the auricular, however the device will be off during the 60 min session.

Data for this study will be collected from subjects using an electronic format capture system (REDCap), and each subject will be assigned a de-identified code to collect the data. The data entered will be securely transferred to the Mass General Brigham REDCap database, to which only IRB-trained and approved study staff will have access. The following assessments will be performed:

Demographic data: This survey will ask about demographic characteristics, including age, gender, sex, race, ethnicity, educational level, hand dominance, weight, height, and body mass index.

Medical history form: We will ask the history of medical conditions, a list of medications currently used, allergies, history of hospitalizations or visits to an emergency room in the last year, tobacco and alcohol consumption, and emergency and primary care physician contact.

BDI: This self-report inventory consists of 21 multiple-choice questions and is a widely used method to classify depression severity. It assesses the presence of several symptoms related to depression, such as irritability, hopelessness, and decreased cognitive performance. Physical symptoms such as weight loss and fatigue are also included.

EHI/SF: This short-form, self-report measure will be used to assess handedness in participants, asking their hand preference for 4 everyday tasks: writing, throwing, using a toothbrush, and using a spoon.

Eletroencephalogram: We will record the EEG using a 64-channel EGI system (Electrical Geodesics, Inc) (EGI, Eugene, USA) in resting and continuously during visual task stimulus presentation.

EEG phase synchronization of the DMN will be assessed in resting state with particular interest in the connectivity between mPFC to other brain regions in this network. EEG will be recorded using a high-density electrode array from two resting state conditions: eyes-open and eyes- closed. Oscillatory activity will be measured in the regional sources of interest that comprises nodes from the DMN, and phase synchrony between DMN regions of interest with reference to the medial prefrontal regions using phase-locking value (PLV). A data-driven statistical approach will be used to analyze the effects of taVNS on PLV. PLV, a measure of phase synchrony (i.e., the average of phase angle difference between two time series), can examine the synchronization in oscillatory activity between brain sources representative of the DMN (57). PLV can range from 0 to 1, with values close to 1 indicating strong synchronicity (i.e., perfect phase locking), while values close to 0 indicate substantial phase variation between the two signals, and thus low synchronicity between the two regions (i.e., no phase synchrony and randomly dispersed phases). To transform EEG data from scalp electrode space into source space, we will use a Matlab to model resting state activity representative of the DMN.

The DMN resting state montage comprised six regional sources of interest: medial prefrontal cortex (mPFC), posterior cingulate cortex (PCC), left and right Angular Gyru (AG), and left and right lateral temporal cortices (LTC). As the multiple discrete sources approach is applied to source montages (58), activity from other brain areas can affect source waveforms of the DMN sources if only these DMN sources of interest are included in the source montage. Therefore, six additional noise sources were also included in the montage to measure brain activity that were not part of the networks associated with resting state activity in the DMN and to increase the sensitivity of the sources of interest. These noise sources comprised left and right occipital sources, left, right, and midline frontal sources, and a middle parietal source. To measure PLV, a complex demodulation method with 0.5 Hz wide frequency bins and 100 ms time resolution in the range of 1 to 50 Hz is used for decomposing the single-trial EEG data into 2-second time-frequency representations of temporal spectral evolution (TSE, an equivalent measure of oscillatory power) normalized to the power spectrum per participant. PLV will be measured from the radial component of each source of interest relative to the mPFC source as the seed (i.e., between mPFC and each of the sources at the PCC, left/right LTC, and left/right AG).

Functional connectivity: Fourier transformation (STFT) will be applied to filter the data into five typically analyzed frequency bands, delta (0.5–4 Hz), theta (4–8 Hz), alpha (8–13 Hz), beta (13–30 Hz) and gamma (30–80 Hz) bands, then we will apply the phase lag index (PLI) method to calculate the connectivity matrices and graph theory-based methods to measure the topology of brain networks across different frequency bands.

In this study, phase synchronization will be measured between all the pairs of channels by the Phase Length Index method, which is an asymmetry index that measures the distribution of phase differences (59, 60). Due to the instantaneous spread of current, the same sources collected by two electrodes are considered to cause a zero-lag phase difference, which is rejected by PLI. Therefore, PLI is less sensitive to the volume conduction effect, and it can reveal the true coupling strength between pairs of channels. The value of PLI index varies between 0 and 1. A value of 0 indicates no coupling or coupling with a phase difference centered around 0 mod p, and a value of 1 indicates perfect phase synchronization between two signals at a constant lag except 0 or p.

Frontal alpha asymmetry (FAA): After transforming to average reference, the continuous EEG signal will be segmented (1000 ms after stimulus onset), Fast-Fourier will transform after the data had been weighted with a Hamming window that tapered the distal 5% of each epoch and averaged without overlap. As the result of the weighting functions in the windowing process, the ends of any 1000 ms-segment will be less weighted.

Power for theta (4-7 Hz), alpha-1 (8-10 Hz), and alpha-2 (11-13 Hz) frequency bands will be extracted separately for happy and sad face stimuli for the left (mean of F3, F5, and F7 electrodes) and right (mean of F4, F6, and F8 electrodes) frontal hemisphere for further statistical analysis.

Tasks and Stimuli

1) The task will consist of alternating trials showing a consecutive series of either sad or happy facial expressions randomized by sex. One trial consists of a series of five to eight faces of one emotion with a varied number of faces per emotion to maintain subjects' attention on the task. To further enhance attention, Participants will be instructed to press a button as they noticed a switch from one emotional expression to the other, i.e., switch from the happy to the sad or from the sad to the happy trial. After six trials, the participants will be asked, "To what extent were you able to emphasize with the faces?" followed by a short break of about 10 seconds until the next six trials are presented. Subjects will need to self-report to what extent they fell empathy towards the face stimuli on a Likert scale ranging from 1 (very much) to 4 (very little). There will be two long breaks of about 20 seconds. During this break and at the end of the task, participants will be also asked, "How do you feel?". Subjects will self-report how they themselves feel on a Likert scale ranging from 1 (very good) to 4 (very bad). Altogether, there will be 24 trials of sad and 24 trials of happy facial expressions, and 6 short and two long breaks (duration of face stimuli presentation: 1000 ms). We will use happy and sad emotional face stimuli from "The Karolinska Directed Emotional Faces" database (61), which have been evaluated on emotional content, intensity, and arousal.

2) The go/no-go task consists of randomly displayed visually cued tasks, including 150 go trials and 50 no-go trials. Each trial started with a white light presented centrally on a gray background for 1,500 ms, followed by a color cue that subtended 20°. Go trials are cued with a "long green" light presented centrally until the response button is pressed or for 300 ms if there is no response. No-go trials are cued with "short green (50 ms) + short red (100 ms)" lights which are displayed for 150 ms. Trials order is pseudo-random and permuted such that on 15% of trials, a no-go cue is shown after three, five, and seven go trials, and on 10% of trials, a no-go cue is displayed after two, four, and six go trials. Participants are instructed to focus on the white light and press the response button with their right hand as quickly as they could every time the go cue appeared and not to press the button when the no-go cue is shown (62).

Heart Rate Variability (HRV): HRV will be collected with a CorSense (EliteHRV, USA) device (an FDA cleared and validated device) from the third finger of the non-dominant hand following a standardized protocol. The measurements will be taken at baseline, during, and after stimulation. As both short- (5 min) and long- (24 hours) duration ECG are valid options for measuring HRV, the data will be stored in a web-based secure system. The recording will be performed for 5 min minutes as recommended in previous trials (63, 64). The HRV metrics will be: (1) total power ≤ 0.04 Hz; (2) very low frequencies ≤ 0.04 Hz (VLF), (3) low frequencies 0.04–0.15 Hz (LF), (4) high frequencies 0.15–0.4 Hz (HF), and (5) LF/HF ratio, as we performed in previous studies from our group (65, 66); (6) the standard deviation of the R-R intervals (SDRR); (7) the count of R-R intervals that differed more than 50 ms (NN50); (8) the percentage of NN50 (pNN50); and (9) the root mean square of the difference between successive R-R intervals (RMSSD) will be measured. Finally, since the HRV random fluctuations and fractal components, we will perform a non-linear method to calculate the short-term detrended fluctuation analysis (DFA-alpha1) (66-69).

Qualitative sensory testing (QST)

Conditioned Pain Modulation Test (CPM-test): We will follow the adapted protocol by Granot et al., 2008 and Nir et al., 2011(70, 71). We will first determine the pain-60 temperature by applying a thermode on the right forearm and delivering a short heat stimuli generated by a TSA-II Stimulator (Medoc Ltd) using the FDA approved safety temperature range of the device that goes up 48°C (118.4 degrees Fahrenheit), each lasting 7s. Subjects will be asked to rate the pain intensity with a numerical pain scale (NPS). Once determined, we will administer the test stimulus for 30s at that temperature and will be asked to rate their levels of pain at 10, 20 and 30s. For the conditioned stimulus, the left hand of the subject will be immersed in water at 10 to 12°C for 30s. Then, the same temperature will be applied on the right forearm (left hand will still immersed) at 10, 20 and 30s. CPM response will be calculated as the difference between the average of pain ratings from the test stimulus minus the conditioned stimulus.

Temporal Slow Pain Summation (TSPS): Heat pulses will be delivered to the right dominant proximal volar forearm using an appropriate size embedded HP-thermode. We will follow the adapted protocol suggested by Staud et al, 2014, in which the HP-thermode was programmed to deliver pulses rising/fall of 1-2-s, depending on subject's heat-evoked pain threshold, from adapting temperatures to peak temperatures, with a plateau of .7-s(72). Subjects will be trained to determine the temperature necessary to elicit pain-60 (see CPM protocol below). Subsequently, they will receive one train of 15 repetitive heat stimuli at 0.4 Hz to the same area, in which by being suitable for eliciting TSPS in most subjects, it allows the rating of individual pain stimuli and is unlikely to induce peripheral sensitization. TSPS will be calculated as the difference between heat pain rating after the 15th stimulus minus the 1st stimulus

Brief Mood Introspection Scale (BMIS): The BMIS scale is a mood scale consisting of 16 mood-adjectives to which a person responds (e.g., Are you "happy"?). The scale can yield measures of overall pleasant-unpleasant mood, arousal-calm mood, and it also can be scored according to positive-tired and negative-calm mood. Demographic data, medical comorbidities and adverse effects will be assessed using a standardized questionnaire.

Visual Analogue Scale to Evaluate Fatigue Severity (VAS-F): We will use an adaptation of the VAS-F assessing only the first question related to tiredness. The scale consists of 18 items relating to the subjective experience of fatigue. Each item asks respondents to place an "X," representing how they currently feel, along a visual analogue line that extends between two extremes (e.g., from "not at all tired" to "extremely tired"). In contrast to discrete, Likert-type scales, the VAS-F places fewer restrictions on the range of responses available to individuals.

Side Effects Questionnaire for taVNS: After the stimulation session, subjects will complete a questionnaire to evaluate potential adverse effects of taVNS on a 4-point scale (None, mild, moderate, and severe). They will be asked whether they have experienced any side effects in an open-ended manner and they will then be specifically asked about ear pain, headache, tingling, dizziness, skin redness, fatigue, prickling, pressure, itching, unpleasant feelings. If any side effects are reported, the degree of relatedness to the intervention will be assessed on a 5-point scale. This type of adverse events questionnaire has been suggested in our recent systematic review and meta-analysis on safety of taVNS and has been used similarly in all the tDCS studies of the group.

Questionnaire to assess the success of blinding in clinical trials: After the stimulation session, subjects will be asked to guess their treatment assignment, and they may be allowed to express treatment guess or uncertainty, i.e. subjects will be asked to guess their treatment assignment among active, sham or do not know. After that they will be asked how confident they are from 0 to 5 on their choice.

7. Risks and Discomforts

Transauricular vagus nerve stimulation (taVNS): it is a technique that poses a non-significant risk to subjects. The safety of taVNS has been addressed and tested by multiple researchers who have concluded that taVNS, as applied in a manner similar to our proposed protocol, induces only temporary mild effects. A review study in 2018 was the first to systematically report transcutaneous vagus nerve stimulation treatment safety(73). The author concluded that transcutaneous vagus nerve stimulation is well tolerated and safe, with only mild side effects(73). Recently, we have just conducted a systematic review and meta-analysis with 167 clinical trials involving 6,322 subjects, and we concluded that active taVNS and controls were not different in the risk of developing an AE and in the intensity of the events. In general, the incidence of AE was low, being ear pain, headache, and tingling the most frequent ones. No severe adverse event was shown to be caused by taVNS. We also found that more than half of the studies did not mention the presence or absence of AEs, and these studies did not differ from those that reported no AE or the presence of at least one AE regarding sex, age, study design, number of sessions, or parameters, such as stimulation intensity, pulse width, and frequency of the stimulation. Thus, we postulate that taVNS is a safe and feasible treatment option.

Electroencephalography (EEG): The EEG procedures are performed to measure the electrical activity in the brain and to examine the dynamic changes. It also allows for better understanding of the effects of electrical activity generated in different areas of the brain. EEG only measures brain activity and does not induce electrical current. These procedures are non-invasive and have been used extensively in clinical practice for diagnosis of neurological conditions such as epilepsy. Therefore, EEG poses no significant risk or anticipated discomfort.

Heart rate variability (HRV): As the EEG, the electrocardiogram (ECG) device is used to measure the electrical activity in the heart and its variability. ECG only records heart activity and does not deliver any electrical current. The procedure is non-invasive and has been used extensively in clinical practice for diagnosis of heart conditions. Therefore, ECG and the HRV recording poses no significant risk or discomfort to the subjects.

Quantitative sensory testing (QST)

Temporal slow pain summation (TSPS) and Conditioned Pain Modulation (CPM): Temporal slow pain summation (TSPS) is thought to represent summation of C fiber mediated pain and is being used to probe pain processing abnormalities in several chronic pain disorders(74, 75). In this protocol short duration noxious heat stimuli are delivered at 0.4 Hz with the destination temperature set to 44°C, 46°C, and 48°C.

Conditioned pain modulation (CPM) is a laboratory method to evaluate the individual capabilities to inhibit pain. This phenomenon is based on the fact that when a pain test stimulus is given together with a conditioning pain stimulus, the test stimulus is perceived as less painful than when it was given alone. In this protocol the conditioning pain stimulus will be performed by using a cold bath of water set to 12°C (76).

TSPS and CPM have no potential risks and are non-invasive. However, these tests assess pain, so a transitory level of discomfort is expected momentarily. These effects are brief and have no health repercussions. The subject can choose to stop this test at any time if they do not feel comfortable continuing.

Behavioral assessments/Questionnaires: All questionnaires and clinical evaluation scales will be administered in the privacy of a closed room. There are no potential risks posed to participants with respect to behavioral tasks and questionnaires. If participants become fatigued during testing or are uncomfortable answering any personal questions, they will be informed that they are allowed to take a break at any point during the experiment and that they may end their participation at any time.

8. Benefits

The results of this study will provide a ground for future studies and may benefit subsequent future subjects to the application of taVNS therapy.

9. Statistical Analysis

Sample size calculation:

We planned a sample size using the available preliminary data from previous mechanistic studies in taVNS and HRV, and transcranial direct current stimulation (tDCS) and EEG metrics. From our knowledge, there is no previous data on the effects of taVNS in FAA, synchrony of DMN, or functional connectivity. For this reason, we calculated the sample size for these outcomes based on an analogous intervention, the tDCS in the left dorsolateral prefrontal cortex. Based on that, we considered some scenarios based on our aims. We could detect a variety of scenarios and different magnitudes of sample sizes, and we decided to choose a more conservative approach taking in consideration the main outcome domains in EEG and HRV that we aim to test in our study with some the smallest effect sizes calculated (See Table 1). We assumed a type I error of 5% (alpha), a type II error of 20% (beta), and a power of 80%. Therefore, taking in consideration the most conservative scenario, we estimated a sample of 36 subjects. However, we expanded the sample in 20% to account for a conservative attrition rate and to increase power for secondary outcome analysis. Then, we will include a total sample size of 44 subjects, this will lead in 22 subjects each group.

Table 1. Sensitivity analysis for sample size calculation

Questions	Intervention	Previous studies	Study effect size (Cohen's d, 95% CI)	Needed sample size (power 80% and alpha 5%)	Final sample increasing by 20%
Aim 1: One active taVNS session effects on frontal alpha asymmetry (FAA), functional connectivity and phase synchrony of DMN using EEG on a processing emotional facial expressions and a Go/NoGo task.					
Effects in alpha asymmetry modulation	Left tDCS	DLPFC	Liu 2022 (77)	F4-3: 1.03 (0.31 to 1.73)	30 subjects
				F6-5: 0.94 (0.23 to 1.65)	36 subjects (18 each arm)
Effects in gamma band FC between the posterior cingulate cortex and r-IPL	Left tDCS	DLPFC	Koizumi 2020 (78)	Pos-pre: 57.71 (43.16 to 72.24)	2 subjects
Aim 2: One active taVNS session effects in heart rate variability					
Effects in LF/HF ratio	taVNS	Vosseler 2020 (cross-over) (79)	-2.22 (-3.13 to -1.29)	8 subjects	10 subjects (5 each group)
Effects in HF	taVNS	Geng 2022 (cross-over) (20)	13.72 (9.93 to 17.49)	2 subjects	4 subjects (2 each group)
Effects in RMSSD	taVNS	Vosseler 2020 (cross-over) (79)	-1.54 (-2.35 to -0.71)	14 subjects	18 subjects (9 each group)
		Geng 2022 (cross-over) (20)	2.35 (1.36 to 3.32)	6 subjects	8 subjects (4 each group)
Effects in pRR50	taVNS	Geng 2022 (cross-over) (20)	1.53 (0.67 to 2.37)	14 subjects	18 subjects (9 each group)
Effects in SDRR	taVNS	Geng 2022 (cross-over) (20)	2.79 (1.72 to 3.83)	6 subjects	8 subjects (4 each group)

Effects in total power	taVNS	Geng 2022 (cross-over) (20)	1.01 (0.22 to 1.80)	32 subjects	38 subjects (19 each group)
------------------------	-------	-----------------------------	---------------------	-------------	-----------------------------

AIM 1: Data forms and questionnaires will be coded in a standardized manner, and double-entered into our database. Digital measures/recording will be similarly tracked in our database and regularly backed up. Analyses will be conducted using standard statistical software such as STATA and MATLAB toolboxes. All analyses will be performed on an intention-to-treat basis (using the method of multiple imputations for missing data). We will also perform an additional sensitivity analysis using completers only. The primary outcomes for this aim will be the EEG biomarkers (alpha asymmetry, functional connectivity, and phase synchrony of the default mode network). We will obtain all the measurements at baseline and during the stimulation period. Linear mixed models will be used to test for differences between the active and sham group, adjusting for covariates when necessary. Further exploratory analysis to detect predictors of response to taVNS will be performed taking in consideration the covariates assessed. Statistical significance will be considered if p-values < 0.05.

The between subjects' factor and measures on hemisphere (left and right), and emotion (happy and sad) will be performed for alpha-1, alpha-2, and theta. All the power will be ln-transformed. The significant main effects will be further analyzed with Cohen's d effect sizes and the interactions will be divided in simple effect and graphical interpretations.

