
Additionally, we aim to assess the effects of taVNS in healthy subjects after one single session in some exploratory related outcomes.

3. General Description of Study Design

We will perform a randomized double-blind sham-control trial. We will randomize 44 healthy subjects, who will receive one single session of active taVNS or sham taVNS at the Neuromodulation Center/ Cambridge Spaulding Hospital.

Mass General Brigham Institutional Review Board
Intervention/Interaction Detailed Protocol

	Consent and Screening	Baseline	Intervention	Post intervention
	Visit 1 (online)	Visit 2	Visit 2	Visit 2
Demographics	X			
Medical History	X			
Consent form	X			
Beck depression inventory	X			
EHI/SF	X			
Pregnancy test	X			
BMIS		X		X
VAS-F		X	X	X
EEG		X	X	X
HRV		X	X	X
QST		X		X
Side Effects Questionnaire for taVNS				X
Success of blinding questionnaire				X
Active taVNS			X	
Approximate visit time	60 min	60 min	60 min	30 min

Table 1: Visits Schema

4. Subject Selection

In this study, we will randomize 44 healthy subjects, and they will need to meet the following inclusion criteria and none of the following exclusion criteria:

Inclusion Criteria:

1. Able to provide informed consent to participate in the study.
2. Subject is older than 18 years.
3. Subjects should be naive to the stimulation (taVNS)

Exclusion Criteria:

1. Pregnancy.
2. Subjects who have had a neuropsychiatric or a cardiac disorder diagnosis and have received treatment and chronic medication in the past six months, or who have functional deficits as a result.
3. History of alcohol or drug abuse within the past 6 months as self-reported.
4. Presence of the following contraindication to transauricular vagus nerve stimulation
 - a. Ferromagnetic metal in the head and in the cranium (e.g., plates or pins, bullets, shrapnel)
 - b. Implanted cranial electronic medical devices (e.g., cochlear implants)
 - c. Implanted cardiac devices (e.g., pacemaker)
5. Unstable medical conditions (e.g. uncontrolled diabetes, uncompensated cardiac issues, heart failure or chronic obstructive pulmonary disease).
6. Uncontrolled epilepsy, as defined by previous clinical seizure in the past 3 months in patients with treatment for epilepsy.
7. Suffering from severe depression (as defined by a score of >30 in the Beck Depression Inventory).*

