When contacting subjects by email, we will communicate through the Massachusetts General Brigham network as per the institutional policy regarding secure email communication using encryption by Mass General Brigham / Partners Healthcare “Send Secure” function. If the first method of contact with the subject is through email, we will explain that they will receive encrypted emails going forward. This initial unencrypted email will have instructions on how to open encrypted emails. We will also explain that they can opt out of secure emails after informing them of the possible security risks. If they choose this option, this preference will be noted in our contact log.

The online informed consent will be obtained by the study PI and/or a co-investigator using the REDCap platform approved by Massachusetts General Brigham network (MGB REDCap eConsent). The PI will be available if the subject wants to discuss the trial with them or have any questions. The study procedures will be described, and the equipment will be shown to the subject. Study co-investigators will clearly explain all the procedures and risks of the testing outlined in the consent form. The subject will be given the time needed to consider their decision and will be encouraged to ask questions, both during the initial online interview (phone or Zoom Enterprise call) and throughout the study. The PI or a co-investigator will answer any questions regarding the study at the time consent is given. Once enrolled, the subject may pause or terminate his/her participation at any time during the study.

5. Subject Enrollment

We will enroll up to 60 subjects to find about 44 subjects, that will be randomized (by web-based program randomization.com) into 2 Groups (allocation ratio 1:1): active taVNS group (active taVNS) or sham taVNS group (sham taVNS). Randomization order will be placed into sequentially numbered sealed envelopes by an otherwise uninvolved staff member. Allocation concealment will be maintained throughout the study. Blinding will be maintained for participants and co-investigators not performing taVNS, including outcome assessors.

All study procedures will be done at the Spaulding Neuromodulation Center/Spaulding Cambridge Hospital.

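### The post-session order is not fixed, and the procedure list puts the side-effects checklist and allocation guess before the self-rated pain, mood and tiredness measures

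*Combined protocol and SAP*

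**What the plan says.** The Visit 2 part of Section 6 opens its post-session list with "After the session, subjects will complete the following assessments". The first two bullets are "Side Effects Questionnaire for taVNS" and "Questionnaire to assess the success of blinding in clinical trials". EEG, HRV, QST, BMIS and VAS-F follow. The bullets carry no numbers or clock times, and no statement that they are in sequence.

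The instrument descriptions later in Section 6 place both forms after stimulation but not relative to the other measures. For side effects: "After the stimulation session, subjects will complete a questionnaire to evaluate potential adverse effects of taVNS on a 4-point scale". For blinding: "After the stimulation session, subjects will be asked to guess their treatment assignment, and they may be allowed to express treatment guess or uncertainty". The response options are given as "subjects will be asked to guess their treatment assignment among active, sham or do not know", followed by a confidence rating from 0 to 5. The side-effects form starts with an open question and then asks about named sensations, including ear pain, tingling, prickling and skin redness.

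The visit table in Section 3 has the row "Success of blinding questionnaire" below the rows for BMIS, VAS-F, EEG, HRV, QST and side effects.

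On masking, Section 5 states: "Blinding will be maintained for participants and co-investigators not performing taVNS, including outcome assessors".

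**The concern.** Three post-session measures depend on what the participant reports: the QST pain ratings (CPM and TSPS), the BMIS mood adjectives and the VAS-F tiredness item. The face task also contains self-ratings of empathy and feeling, which would be in the same position if that task is repeated after the session. A participant who has just been asked about tingling and ear pain, and then asked to name an arm and say how sure they are, may rate these items with that answer in mind.

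The design makes this more than a formality. Section 6 sets the stimulation intensity individually for each participant, through two rising series of short trials taken to the point of discomfort. In the sham arm the device is then off for the whole hour. A sham participant may therefore have felt real stimulation beforehand and feel none in the session, so guessing better than chance is plausible. The checklist directs attention to the very sensations that separate the arms.

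At stake is how the post-session differences in pain, mood and tiredness are read. Part of any difference could come from the prompt rather than from the stimulation.

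**Working it through.** No arithmetic in the plan bears on this point, so the check compares the two lists and then asks which analyses could be affected.

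**1. The same seven post-session items in each place**

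| Position | Section 6 post-session list | Section 3 visit table, post-intervention column |
|---|---|---|
| 1 | Side effects | BMIS |
| 2 | Blinding guess | VAS-F |
| 3 | EEG | EEG |
| 4 | HRV | HRV |
| 5 | QST | QST |
| 6 | BMIS | Side effects |
| 7 | VAS-F | Blinding guess |

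The two forms are first in one place and last in the other. EEG, HRV and QST keep their positions, and side effects come before the guess in both.

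**2. Does either place prescribe an order?** The table does not. Its active taVNS row sits below the post-intervention questionnaires, and demographics sit above consent, so its rows are not chronological. Its baseline rows (BMIS, VAS-F, EEG, HRV, QST) also differ from the Section 6 baseline list (EEG, HRV, QST, BMIS, VAS-F). The Section 6 list does not claim to be a sequence either, and the intensity-setting done on arrival is described after it. It is, however, the only narrative list of post-session procedures, and no text tells staff to hold the two forms back.

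**3. Which analyses could be affected?**
- Aim 1 EEG: Section 9 takes these measurements at baseline and during stimulation, before either form. Not affected.
- Aim 2 HRV: the after-session value is used, but it is recorded by a device and is not a self-rating.
- QST, BMIS and VAS-F: they are in neither numbered aim; Section 2 refers only to exploratory related outcomes. Their post-session values are exposed. VAS-F is also taken during stimulation, and that reading precedes any guess.

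**4. What determines the size?** Let a1 and a0 be the shares answering active in the active and sham arms, and s1 and s0 the shares answering sham. Let dA and dS be the extra shifts in a rating caused by being prompted to say active or sham, beyond what the participant already believed. Then

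added contrast = (a1 − a0) × dA + (s1 − s0) × dS.

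An answer of do not know is taken to add no shift. If guesses are unrelated to allocation, then a1 = a0 and s1 = s0, and the added contrast is zero. The documents give none of these six quantities, so no value can be computed.

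**The case against.** The strongest reply is that no order is prescribed, so no bias has been built in. Unnumbered bullets are not a running order, and the site may already leave the two forms to the end. This is right as far as it goes. It leaves the protocol silent on a point where its only narrative list suggests the less favourable order.

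A second reply is that awareness of allocation arises during the session, whatever the order of the forms. This also stands. Reordering removes only the part added by the prompt.

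Four stronger readings are tempting, and the documents do not support them.
- A reader might infer that the table and the list contradict each other. The table is not chronological, so its row order is no rival instruction.
- A reader might infer that every participant declares an arm before the ratings. That treats the list as a sequence and overlooks the do-not-know option.
- A reader might assume a rate of correct guessing and a shift in ratings, and convert them into an inflated false-positive rate. Neither input is in the documents, and such a figure would charge all awareness of allocation to the order of the forms.
- A reader might infer that the forms disturb resting HRV or unmask the QST assessor. No text shows that the forms affect HRV, or that the assessor administers or sees the checklist.

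**Conclusion.** The point holds as a gap with a cheap remedy. The protocol does not fix the post-session order, and its procedure list, if followed, takes the pain, mood and tiredness ratings straight after a prompt about sensations and allocation. This could add to any active-sham difference that unblinding already produces in those ratings.

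The conclusion rests on two conditions: that staff follow the list as printed, and that guesses are related to allocation. The second is plausible with a device-off sham after individual intensity-setting, but it is not shown. The size is unknown and may be zero. The exposure is confined to subjective, exploratory post-session ratings, and the Aim 1 EEG results are untouched.

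**What to change.** State one post-session sequence in the Visit 2 part of Section 6, and make the Section 3 table and the two questionnaire descriptions agree with it:

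1. EEG, HRV, QST, BMIS and VAS-F.
2. The side-effects checklist.
3. The blinding guess and confidence rating, last.

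Have the participant complete both forms directly in REDCap, so that the outcome assessor does not see the answers before the outcomes are recorded. The person who delivered the stimulation should not collect them. That person is outside the blinding described in Section 5, and could influence both the rating of how far a side effect is related to the intervention and the guess itself. Complaints that a participant volunteers are still recorded whenever they occur.

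The change adds no visit, form or analysis. Its cost is that the checklist and the guess are recorded up to about 30 minutes later, which is the post-intervention time in the visit table, and that the guess may be slightly coloured by the tests in between.
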